1.2 Quantitative Analysis Plan

The primary hypothesis is that due to developing skills in self-management and assertive communication, inclusion of adjunct components will be associated with clinically significant decreases in HIV transmission risk behavior (TRB) as compared to partnered YMSM who receive CHTC (only). Secondarily, we propose that these intervention effects will be mediated by assertive communication skills. As stated above, we focus on four behavioral indicators of TRB. At the individual-level, we examine: (1) number of CAS acts with a casual partner in the absence of PrEP and (2) any positive chlamydia or gonorrhea diagnoses in the absence of PrEP. At the couple-level, we will examine (3) any sex in the absence of PrEP with a primary partner who reports CAS with a casual partner; and (4) any sex in the absence of PrEP with a primary partner who receives a positive chlamydia or gonorrhea diagnosis. Any missing data and additional covariates will be informed by attrition analyses prior to primary analyses.

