1.2.1 Analytic Plan

All primary outcome variables will be tested in the context of a multilevel growth model, which accounts for the nesting of individuals within couples. In order to capture within-individual change over time, we will utilize a latent growth curve approach to modeling follow-up data. At the individual level (Level I), models will include an intercept and linear slope component to represent the initial value and change over time in each participant's outcome. We will explore the inclusion of quadratic components as indicated by model fit. Mplus provides the flexibility to accommodate count and dichotomous outcomes. Growth factors will then be regressed on intervention condition at the couple level (Level II) and the effect of the intervention will be evaluated by examining the regression coefficient (and associated *p* value) associated with intervention condition for each of these factors.

Secondary analyses of individually reported self-management and dyadic functioning as potential mediators of the intervention's effect on TRB will specify growth factors for self-management, dyadic functioning, and communication skill scores during the follow-up period. In this manner, growth factors for the outcome can be regressed on growth factors for the putative mediator. Intervention effects (a couple-level predictor) will be determined by examining regression coefficients associated with intervention in the prediction of growth factors for both

the outcome of interest and mediator. For significant direct effects, indirect path from intervention communication will be tested using bootstrapping tests of mediation. Where outcome distributions prevent bootstrapping, we will utilize a model constraint approach to evaluate significance of indirect effects. The product of constituent direct effects is constrained as zero. The overall model fit under this constraint is compared to one where the constraint is not specified. A statistically significant reduction in fit associated with constraint represents evidence that indirect effects differ from zero[53].

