1.2.2 Equivalency Tests

We will follow standard procedures in cleaning data and examining initial distributional properties (means, standard deviations, medians, skew, kurtosis) in addition to graphical summaries (boxplots and density plots). Subsequently, we will evaluate the success of randomization by testing between-condition differences with respect to demographic covariates and primary outcomes reported at baseline. Note, because participants are nested within dyads, these analyses will utilize the Generalized Estimating Equation (GEE) module within SPSS to

control for the non-independence of observations and specify outcome distributions that are appropriately matched to the variables of interest.

Finally, we will conduct an analysis of attrition to determine if dropout at each follow-up time-point is associated with (1) demographic variables assessed at baseline and/or (2) drug use or TRB outcomes assessed at baseline. At each wave, we will utilize GEE models to evaluate whether those participants retained at the given wave differ significantly with respect to demographic or baseline outcome values compared to those who were not retained. As with the analyses of randomization success, the use of GEE permits analyses to control for the nesting of participants within couples and specify outcome distributions that are matched to variables of interest. Factors which are observed covary significantly with attrition will be incorporated as covariates in outcome analyses. Mplus has a variety of options for handling partial attrition including full-information maximum likelihood estimation [56]. Non-random and consequential missingness can also be modeled directly through the addition of latent variables which account for the probability of missingness at any time point. Where indicated, we will explore the use of these procedures in the analyses described below.

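### SAP 1.2.1 does not commit the primary model to the four Phase 3 randomisation strata, because covariates other than condition enter only through dropout tests

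*SAP*

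**What the plan says.** Protocol 6.0 (Randomization Stratification) stratifies on four factors: site, age (whether either partner is a minor), race/ethnicity (whether both partners are White), and whether the index partner came alone or as part of a couple.

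SAP 1.2.1 specifies the treatment test as follows: "Growth factors will then be regressed on intervention condition at the couple level (Level II". It names no other predictor for the primary model.

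Two statements govern further covariates. SAP 1.2 says "Any missing data and additional covariates will be informed by attrition analyses prior to primary analyses". SAP 1.2.2 (Equivalency Tests) says "Factors which are observed covary significantly with attrition will be incorporated as covariates in outcome analyses". The candidates for those dropout tests are listed as "1) demographic variables assessed at baseline and/or (2) drug use or TRB outcomes assessed at baseline". The same section plans "testing between-condition differences with respect to demographic covariates and primary outcomes reported at baseline", but attaches no consequence for the model to the result.

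On the time axis, SAP 1.2.1 says "we will utilize a latent growth curve approach to modeling follow-up data", and also that "models will include an intercept and linear slope component to represent the initial value and change over time". It does not say whether the initial value is the baseline visit or the first follow-up.

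**The concern.** The design forces balance on four factors and the analysis as written does not use them. When such factors predict outcome, the unadjusted standard error still contains variation that the randomisation has removed from the treatment comparison. The test then rejects too seldom under the null and has less power than the design allows.

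The one route by which covariates can enter screens for association with dropout. That is not a screen for prognostic value, and it leaves the covariate set open until follow-up ends. SAP 1.2 speaks of additional covariates without naming a base set to which they are added.

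There is little power to spare. The SAP's power claim was computed for 288 individuals, and Protocol 12.0 enrols 200 in Phase 3.

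**Working it through.** **1. The strata against the SAP.**

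| Factor | Fixed in SAP 1.2.1? | Named as a dropout-test candidate? |
|---|---|---|
| Site | No | No |
| Age | No | Possibly, as a demographic |
| Race/ethnicity | No | Possibly, as a demographic |
| Individual or couple attendance | No | No |

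**2. The plan's own figure.** SAP 1.2.2 (Power Analysis) states power above .80 with 288 individuals, at least 232 of them retained. This cannot be reproduced, because the control risk, within-couple correlation and growth-factor variances are not given. A two-proportion calculation at one wave used 232 individuals, odds ratio 1 - 0.56 = 0.44, control risk 10-50%, and design effect 1 + ICC with ICC 0 to 0.5. It gives power from 0.25 to 0.86, which neither confirms nor refutes the claim.

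**3. Analysed number.** Planned retention is 232/288 = 80.6%. Applied to 200 this gives 200 x 232/288 = 161.

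**4. Mechanism.** Let R² be the share of outcome variance explained by the strata (linear approximation). With balance on the strata, the true variance of the treatment estimate is proportional to 1 - R². The unadjusted standard error is computed as if it were proportional to 1. The test is therefore conservative whenever R² > 0.

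**5. Single-wave simulation.** There were 20,000 replicates per setting. The 3 x 2 x 2 x 2 = 24 cells were randomised in blocks of 4 (assumed). Of 200 randomised, 161 were kept at random. The outcome was binary with clustering ignored, analysed by a logistic Wald test. The conditional odds ratio of 0.44 is borrowed from the ACT pilot, which is not the Phase 3 contrast. Control risk (30%) and the log-odds effect g per stratum are assumptions. With the binary strata split 50/50:

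| g | Site effects | Type I error, unadjusted / adjusted | Power, unadjusted to adjusted | Gain (points) |
|---|---|---|---|---|
| 0 | none | 4.8% / 5.0% | 57.1% to 58.0% | 0.9 |
| 0.5 | 0, g/2, g | 4.3% / 5.0% | 53.4% to 56.0% | 2.6 |
| 0.5 | 0, g, 2g | 4.5% / 5.4% | 53.0% to 56.3% | 3.3 |
| 1.0 | 0, g/2, g | 3.6% / 5.3% | 46.5% to 53.0% | 6.5 |
| 1.0 | 0, g, 2g | 3.1% / 5.0% | 41.5% to 50.6% | 9.1 |

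Hand check of the first row: the treated risk is (0.3/0.7 x 0.44)/(1 + 0.3/0.7 x 0.44) = 0.159. With 80.5 per arm, SE = √[(0.3 x 0.7 + 0.159 x 0.841)/80.5] = 0.065. Then z = 0.141/0.065 = 2.16, and power is about Φ(2.16 - 1.96) = 0.58.

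Adding an unequal mix (age 20%, race 30%, couple 30%), the gains at 30% control risk are 0.9, 2.2-3.4 and 6.1-9.1 points for g = 0, 0.5 and 1.0. Over control risks of 20-50% they are 0.6-1.4, 2.2-3.6 and 5.6-10.6 points. Adjusted type I error across the single-wave runs is 4.8-5.5%.

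**6. Three-wave check.** There were 4,000 replicates of 154 index participants, 30% attending as couples (154 x 1.3 = about 200 individuals). Assumed retention was 95, 88 and 80.6% at months 1, 3 and 6, and assumed random-effect SDs were 0.6 (couple) and 1.0 (person). The model was a cluster-robust logistic with time zero at month 1.

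- Intercept coefficient, g = 0, 0.5, 1.0: power 56.4 to 57.5%, 55.0 to 58.0% and 43.4 to 54.2%, gains of 1.1, 3.0 and 10.8 points.
- Slope coefficient, with strata shifting level only: 34.2 to 34.0%, 31.9 to 31.9% and 30.0 to 30.4%, so no gain.
- Type I error, intercept: .047, .052 and .031 unadjusted; .049, .062 and .054 adjusted. Monte Carlo error is √(0.05 x 0.95/4000) = 0.34 points, so .062 is high for chance. A repeat with 6,000 replicates under the same main assumptions gave .042 unadjusted and .050 adjusted at g = 0.5, with power 52.4 to 56.6%.

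**7. Cost in parameters.** Site 3 - 1 = 2, and the other three factors 1 each: 5 per adjusted growth factor. Fitting all 24 cells would leave 161/24 = 6.7 people per cell, which argues for main effects.

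**The case against.** The strongest defence concerns the purpose of the dropout rule. SAP 1.2.2 (Equivalency Tests) places it beside full-information maximum likelihood, where conditioning on predictors of dropout supports the missing-at-random assumption. With planned loss of 1 - 0.806 = 19.4%, that matters. A missing-data device should not be faulted for failing to be a precision device. This stands: a reader might infer that the dropout-associated covariates should be demoted to a sensitivity analysis, but adding the strata does not require it.

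The gains are also hypothetical. The largest need every stratum to act at once at log-odds 1.0. With site effects 0, g, 2g, that puts two sites exp(2) = 7.4 apart in odds. Even at g = 0 the gain is 0.9 points, so about that much is not prognostic information. The simulated outcome is binary, whereas outcome 1 is a count, and the slope test gains nothing. All of this stands as a limit on size.

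The SAP may also describe another version of the design. It plans 144 couples against CHTC alone; the protocol plans 200 individuals against IHTC. Attendance mode would have no place in an all-couples trial. That may explain the omission but does not fill it.

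Two other inferences are tempting. One is that omitting the strata biases the treatment effect or inflates false positives. The simulations show the reverse for false positives. The dropout rule does not look at the treatment effect. An odds ratio nearer 1 without the strata reflects the difference between a marginal and a conditional effect. The other is that baseline outcomes are left out of the model. The reference to "communication skill scores during the follow-up period" for the mediators and the three follow-up points in the power section suggest a follow-up-only series, but the initial value in SAP 1.2.1 can equally mean baseline. The text does not settle it.

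**Conclusion.** The point holds as one of efficiency and pre-specification. Nothing in either document commits the primary model to the stratification factors. Age and race/ethnicity may enter by way of dropout; site and attendance are not named at all.

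The size cannot be derived from the documents. At 30% control risk it is about 1, 2-3 or 6-9 power points in a single wave for assumed stratum effects of 0, 0.5 or 1.0. It is similar on the intercept factor over three waves, and nil on the slope if strata shift level only. Adjusted type I error is about 5%; the one run at .062 was not borne out on repetition. The change is worth making because power is already short and the factors are recorded at randomisation. The validity of the trial does not depend on it.

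**What to change.** In SAP 1.2.1:

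1. Include site, age stratum, race/ethnicity stratum and individual/couple attendance as fixed covariates in every primary model, at least on the intercept factor, whatever the dropout tests show. Use the values recorded at randomisation and do not update them if a partner joins later. Enter main effects, not 24 cells, and collapse sparse levels.
2. Keep the dropout-associated covariates of SAP 1.2.2 (Equivalency Tests) in addition, for their missing-data role.
3. State where the modelled series starts. If it starts at the first follow-up, add the pre-randomisation CAS value as a covariate for outcome 1, for participants whose survey preceded randomisation. A late-joining partner's first assessment does not qualify, since Protocol 6.0 places that partner in the condition already assigned to the index. If baseline is the first point of the series, no baseline covariate is needed. No power gain is claimed for this item.

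The change is SAP wording and needs no new data. It costs 5 degrees of freedom per adjusted growth factor, or 6 for outcome 1 if the baseline value is added. It brings some convergence risk for the sparse STI and couple-level outcomes; STI testing has only two post-baseline waves, at months 3 and 6. Odds ratios become conditional on the strata and should be reported as such.

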1.2.2 Power Analysis

Consistent with the intervention development goals of Phase 2, we are not powered to detect significant between-condition differences in primary outcomes for that phase. Power analyses for Phase 3 were conducted based on our preliminary pilot data extracted from a similar study (R34 DA036419; PI [name]) testing adjunct CHTC components in emerging adult gay male couples aged 18-29 years. Preliminary results from the 3 month wave of data collection (the most distal available with sufficient data to estimate effects at the time of protocol paper submission) suggested that viewing ACT videos prior to CHTC was associated with a 56% decrease in the odds of CAS with a casual partner (relative to CHTC alone) among HIV negative participants not on PrEP. Of particular relevance to our mediation hypotheses, viewing ACT videos prior to CHTC was associated with a 5 to 6 point decrease in avoidant communication as measured by the Communication Patterns Questionnaire (CPQ) [54]. In turn, CPQ avoidant communication scores had a significant positive association with CAS with casual partners among HIV negative men not on PrEP ($\exp B = 1.06, p < .01$). Separately, our previous study of brief MI interventions with YMSM suggest it is associated with as much as an 83% reduction in the odds of CAS with a casual partner [55] compared to an attention-matched psychoeducation control condition.

These preliminary effect sizes were utilized as parameters in power analyses using a Monte Carlo simulation approach in Mplus (version 7.3)[53]. This approach provides a direct estimation of power while modeling both the multilevel structure of data (individuals are nested within couples) and the longitudinal design of the study (each individual provides data at 3 follow-up points). The program generates random samples from the specified population and, within each sample, examines the significance of freed parameters. Power is defined as the proportion of simulated samples in which the freed parameter has a p value of less than .05. All models specified a random seed and used 10,000 sample replications. Power analyses conducted based on these preliminary effect sizes suggests that $n = 144$ couples ($n = 288$ individuals), anticipating a minimum of $n = 232$ individuals retained at 6 months, is adequate to achieve power $> .80$ for all hypothesized direct effects as well as indirect pathways.

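### Four unranked primary outcomes are each judged on several growth-factor p values, with no decisive contrast, multiplicity control or success rule

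*SAP*

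**What the plan says.** SAP section 1.2 states a single primary hypothesis about transmission risk behavior (TRB) and then says "we focus on four behavioral indicators of TRB". Two are at the individual level: condomless anal sex (CAS) acts with casual partners without PrEP, and a chlamydia or gonorrhea diagnosis without PrEP. Two are at the couple level and depend on the primary partner's casual CAS or the primary partner's diagnosis. None is placed ahead of the others.

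Section 1.2.1 says "All primary outcome variables will be tested in the context of a multilevel growth model". In each model, "models will include an intercept and linear slope component", and then: "We will explore the inclusion of quadratic components as indicated by model fit". The growth factors are regressed on condition, and the effect is evaluated from the coefficient and p value "associated with intervention condition for each of these factors". The same section tests mediation only where a direct effect is significant, without saying which direct effect.

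The only significance level is in the SAP's Power Analysis section: "Power is defined as the proportion of simulated samples in which the freed parameter has a p value of less than .05". Protocol section 4.0 describes the goals in other terms (number of sex acts, receptive intercourse, condom use) and sets no decision rule.

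**The concern.** The plan does not say what pattern of results would support the primary hypothesis. Two analysts who followed it exactly could disagree, for instance over one significant slope among eight coefficients with the other seven null. The number of tests also depends on the data, because the quadratic is chosen by fit.

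Reading each coefficient at .05, the only level given, would let the one hypothesis be called supported at an error rate well above that of a single test. A false positive on any factor could also open the mediation analysis. Protocol section 5.0 plans to package and disseminate components shown to be effective, so the reading of these p values has practical consequences.

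**Working it through.** **Inputs from the documents.** Four outcomes (SAP 1.2). Two growth factors each, three with a quadratic (SAP 1.2.1). Two Phase 3 arms, so one condition contrast per coefficient (Protocol 2.0). Per-parameter level .05 (SAP Power Analysis). Surveys at 1, 3 and 6 months; STI testing at baseline, 3 and 6 months (Protocol 6.0).

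**Assumptions.** Two-sided tests, since sidedness is not stated. Correlation between outcomes of 0 to 0.7 and random-intercept variance of 0, 1 or 3 times the residual variance, since the documents give neither.

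**The plan's own figure.** No familywise error rate is stated, so there is none to reproduce. The stated power (> .80 with 288 individuals, 232 retained, 232/288 = 80.6%) cannot be rerun, because base rates, variances and within-couple correlation are not given.

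**Number of tests.** 4 × 2 = 8 condition coefficients. With a quadratic in every model, 4 × 3 = 12. With a quadratic only in the two non-STI outcomes, 8 + 2 = 10.

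**Independent tests.** The chance of at least one p < .05 under the null is 1 − .95^k. Counting only errors that favour the intervention, it is 1 − .975^k, against 2.5% for a single test.

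| Tests | Either direction | Favourable only |
|---|---|---|
| 4 (slopes only) | 18.5% | 9.6% |
| 8 | 33.7% | 18.3% |
| 10 | 40.1% | not computed |
| 12 | 46.0% | 26.2% |

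**Why independence is too pessimistic.** Outcomes 3 and 4 use the partner's version of outcomes 1 and 2. On the 1, 3 and 6 month schedule, with or without baseline, the linear and quadratic estimates correlate at about −0.97. The STI outcomes have two follow-up points, three with baseline, so a quadratic in all four models is doubtful.

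**Correlated tests.** Normal test statistics were simulated (at least 300,000 draws per scenario). Correlations among growth factors were derived from the visit schedule, and correlations between outcomes ran from 0 to 0.7.

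| Tests | At least one p < .05 |
|---|---|
| 4 slopes | 13-18.5% (15.5% at correlation 0.5) |
| 8 | 20-33% |
| 10 | 22-35% |
| 12 | 24-36% |

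Counting favourable errors only, the same simulation gives about 7-10% for four slopes and 13-19% for eight tests. That is roughly half to two-thirds of the either-direction figures.

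**Cost of adjustment.** Power of .80 at two-sided .05 implies a standardised effect of 1.960 + 0.842 = 2.802. Holm's first step over four outcomes is .05/4 = .0125, with critical value 2.498. Power there is Φ(2.802 − 2.498) = Φ(0.304) = .62.

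**The case against.** Four points on the other side carry weight.

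- **No any-one-wins rule is written down.** Section 1.2.1 says the effect is evaluated by examining coefficients, not that one p < .05 confirms the hypothesis. A reader might infer that following the plan produces the error rates above. The documents do not support that: the figures hold only if any significant coefficient counts. The gap itself stands, because nothing excludes that reading.
- **No familywise 5% is promised.** A reader might infer that a stated 5% is breached. The .05 is a per-parameter level inside the power definition.
- **The 46% figure is tempting but does not describe this plan.** It needs twelve independent tests, and the overlapping outcomes, the near-collinear growth terms and the sparse STI visits rule that out. Every range here also depends on correlations that the documents do not give.
- **The intercept may not be a treatment effect.** If time zero is baseline, a condition difference there is chance imbalance, and only four slopes remain. If time zero is the first follow-up, the intercept does count, and the SAP speaks of modelling follow-up data. The text does not settle this, which is a further reason to define the contrast.

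These points reduce the size of the problem and make it conditional. They do not supply the missing rule.

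**Conclusion.** The concern holds. One primary hypothesis rests on four unranked outcomes and at least eight p values, with no lead outcome, decisive contrast, multiplicity control or success rule. That can be said with high confidence from the text.

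The size is less certain. It is about 20-36% if any p < .05 counts as success, and about 13-18.5% if only the slopes count, with lower figures for favourable errors alone. All of these rest on assumed correlations and two-sided tests. Under each of them the error rate is several times that of a single test, so the rule should be fixed before the results are read.

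**What to change.** Before arm-level results are seen, amend the SAP to:

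1. State where time zero lies, so that a baseline intercept difference is not read as a treatment effect.
2. Name one post-randomisation treatment contrast per outcome, and report the remaining growth factors, including any quadratic, as descriptive.
3. Either designate one primary outcome tested at .05, with the other three secondary in a fixed order or under Holm, or keep all four as primary with Holm across the four contrasts.
4. Say which significant direct effect opens the mediation test.

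The wording is inexpensive, but the change is not free. A single primary outcome loses no power to alpha adjustment. With four under Holm, the first-step power falls from .80 to about .62. Either way the stated power must be rechecked for the chosen contrast. The SAP powered model parameters and not, for example, a 6-month difference, and its CAS effect sizes are odds reductions whereas outcome 1 is a count. The recheck should also settle the Phase 3 sample size (288 individuals in the SAP, 200 in the Protocol) and the comparator (CHTC only in the SAP, individual testing in the Protocol), on which the two documents differ.

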2.0 Objectives*

Aims: We will conduct a comparative effectiveness trial (CET) of Couples HIV Testing and Counseling (CHTC) for adolescent-age (15-24 years) same-sex male couples. This design tests the added benefits of adjunct intervention components delivered prior to receipt of CHTC-Assertive Communication Training (ACT) videos viewed by the couple separately and individually delivered Motivational Interviewing-based Communication Skills Training (MI-CST). These target the development of communication skills necessary to participate fully in HIV prevention and sexual safety discussions inherent to CHTC. This project will assess a continuum of intervention packages to address the developmental needs of YMSM (CHTC; ACT videos + CHTC; MI-CST + ACT videos + CHTC) to identify which package optimizes outcomes while minimizing delivery cost.

Aim 1: Conduct a sequence of randomized control trials (RCTs) to evaluate the acceptability, feasibility, and comparative effectiveness of novel treatment packages.

Aim 1a: In study Phase 2, we will conduct a pilot RCT to evaluate the acceptability and feasibility of adjunct intervention components. This initial trial will recruit n=36 couples who will be randomized to one of 3 conditions: Condition 1: CHTC (only); Condition 2: couples' joint observation of ACT videos + CHTC; Condition 3: each individual within couple receiving MI-CST + joint observation of ACT videos + CHTC. Youth will then complete follow-up assessments at 1 and 3 months post-intervention. YOUTH DO HAVE THE OPTION OF COMPLETING THE INTERVENTION ON THEIR OWN IF THEY CAN NOT GET THEIR PARTNER TO AGREE TO PARTICIPATE. During Phase 3, we will recruit 200 individuals into a CET with two conditions: Condition 1: the optimum adjunct intervention package identified in Phase 2 and Condition 2: Individual HIV Testing (IHTC) as usual. Youth in this CET will complete follow-up assessments at 1, 3, and 6 months. Youth have the choice of attending the baseline visit alone or with their partner and have the option to bring their partner in later after completing the baseline alone.

Aim 1b: Assess self-management model; we posit that assertive communication skills will mediate intervention effects at all follow-ups. In study Phases 2 and 3, we anticipate between-condition differences will be greatest among YMSM with poor baseline assertive communication.

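### The mediation model names no baseline covariate for the non-randomised mediator-to-outcome path, so prior differences between participants can appear as mediation

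*SAP*

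**What the plan says.** SAP 1.2.1 says of the outcomes that "we will utilize a latent growth curve approach to modeling follow-up data", and that "models will include an intercept and linear slope component to represent the initial value and change over time in each participant's outcome". For mediation it specifies "growth factors for self-management, dyadic functioning, and communication skill scores during the follow-up period", then: "In this manner, growth factors for the outcome can be regressed on growth factors for the putative mediator". Condition enters as a couple-level predictor of both sets of growth factors. Where direct effects are significant, the indirect path is tested by bootstrap or, where the outcome distribution rules that out, by constraining the product of paths to zero and comparing fit. No baseline mediator or baseline outcome is named in any of these models.

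Covariates are covered in two other places. SAP 1.2 ties additional covariates to the attrition analyses. SAP 1.2.2 Equivalency Tests says: "Factors which are observed covary significantly with attrition will be incorporated as covariates in outcome analyses". The baseline variables screened for attrition are demographics, drug use and transmission risk behaviour (TRB). The randomisation check covers demographics and primary outcomes. The communication score is on neither list.

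Protocol 2.0, Aim 1b, nevertheless expects baseline communication to matter: "we anticipate between-condition differences will be greatest among YMSM with poor baseline assertive communication".

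**The concern.** Condition is randomised; the mediator is not. The condition-to-mediator and condition-to-outcome effects are protected, but the mediator-to-outcome path is an observational association within the trial. Participants who communicated poorly and took more risk before randomisation will tend to do both afterwards. This alone can make the path non-zero, even if changing communication changes nothing. Multiplied by a real intervention effect on communication, it gives an indirect effect that does not exist. The bootstrap and the constraint test both ask whether the product is zero, so neither reveals the confounding.

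Mediation by assertive communication is the stated secondary hypothesis in both documents and part of Aim 1b. At stake is a conclusion that the package works through communication skills when it does not.

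**Working it through.** **1. The plan's own figures.** SAP 1.2.2 Power Analysis claims power above 0.80 for all direct effects and indirect pathways, from a Monte Carlo simulation. This cannot be reproduced: comparator risk, couple-level correlation, growth variances and the standard deviation (SD) of the Communication Patterns Questionnaire (CPQ) score are not given. The implied size of the indirect effect can be worked out from three inputs in that section:

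- condition to mediator: a fall of 5 to 6 CPQ avoidant points
- mediator to outcome: exp B = 1.06 per point
- condition to outcome: 56% lower odds of condomless anal sex (CAS) with a casual partner, so OR = 1 − 0.56 = 0.44

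Indirect OR = 1.06^(−points): 1.06^(−5) = 0.75 and 1.06^(−6) = 0.70.

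Share of the total log-odds effect = points × ln(1.06) / −ln(0.44): 5 × 0.0583 / 0.821 = 0.35 and 6 × 0.0583 / 0.821 = 0.43.

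So 35% to 43% of the assumed effect runs through a coefficient that the SAP reports only as an association ("CPQ avoidant communication scores had a significant positive association with CAS with casual partners"), with no mention of baseline adjustment.

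**2. How often mediation is falsely declared (CPQ scenario).** Assumptions not in the documents: CPQ SD 10, baseline-to-follow-up correlation 0.5 to 0.7, comparator risk about one third, independent individuals, one follow-up value. Condition lowers follow-up CPQ by 5.5 points and has OR 0.44 on CAS; follow-up CPQ has no causal effect. CAS depends on pre-randomisation communication, scaled so that the follow-up association is about 1.06 per point. The mediator model is linear and the outcome model logistic, with a 95% Monte Carlo interval for the product. Results at n = 200, rounded over repeated runs:

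| Case | Mediation falsely declared |
|---|---|
| No baseline adjustment, measured baseline is the confounder, all of the association confounded | about 85% |
| Same, a significant condition effect on the outcome required first | about 50% to 55% |
| No adjustment, half of the association confounded | about 36% to 41% |
| No adjustment, a quarter confounded | about 12% |
| Both baselines added, measured baseline is the confounder | about 5% |
| Both baselines added, baseline a noisy marker of a stable trait, all confounded | about 20% to 40% |

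Sensitivity of the unadjusted, fully confounded case (correlation 0.5, no prior significance requirement): 51% at SD 6, 51% at SD 20, 58% at comparator risk 0.15, 41% at risk 0.10, and 31% with SD 6 and risk 0.15 together.

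**3. A second design.** This used the mean of three follow-up waves in place of the latent factor, and required both paths to be significant. It assumed a 0.5 SD intervention effect on communication and a baseline communication–outcome correlation of −0.3.

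- Baseline fully carries the prior differences: 31% (N = 200) and 41% (N = 288) unadjusted; 5.9% and 4.5% with both baselines.
- Stable traits, baseline reliability 0.6: 90% and 97% unadjusted; 22% and 28% with both baselines.
- Baseline correlation set to zero: 5% to 6%.
- No intervention effect on communication: about 6% or less.

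The last two lines confirm the mechanism: a false indirect effect needs both prior confounding and a real intervention effect on the mediator.

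**The case against.** The strongest points on the other side, and what stands of each:

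- **Time zero.** SAP 1.2.1 says the intercept represents the initial value, which could mean baseline is the first modelled wave. The text does not define time zero, so this reading is open. However, the mediator factors come from "communication skill scores during the follow-up period" and the power section counts three follow-up points, which favours a post-baseline start. Nor would that reading settle the matter: in the second design, regressing change on change with baseline as wave zero, but without the baseline levels as predictors, still gave 27% (N = 200) and 41% (N = 288).
- **Baseline outcome may enter.** Baseline TRB is adjusted for if it predicts attrition. Its absence is therefore the default and not a certainty. This does not help the communication score.
- **The significance condition.** The indirect path is tested only after significant direct effects. If that means the condition effect on the outcome, the fully confounded rate falls to about 50% to 55%. If it means the two constituent paths, it hardly changes. The SAP does not say which.
- **Proxy models.** The simulations are simpler than a multilevel growth model with intercept and slope factors, and their inputs are largely assumed. This stands: they show direction and rough size only.

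A reader might infer that the trial would falsely report mediation about four times in five. The documents do not support that. They do not say how much of the 1.06 association is confounded or whether the earlier study adjusted for baseline, and the high figure assigns all of it to prior differences. A reader might also take the problem to be imbalance between arms. It is not: chance imbalance is small at this size, and the bias arises with perfectly balanced arms.

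**Conclusion.** The point holds as a gap in the specification of a secondary analysis. As written, the mediator-to-outcome path is open to confounding by differences between participants that predate randomisation, so the mediation hypothesis can be confirmed when it is false. How often depends on the share of the association that is confounded, the CPQ SD, the stability of the score, comparator risk and the reading of the significance condition, none of which the documents settle. About 12% to 85% at n = 200 is an illustrative range with measured baseline as the confounder, not an estimate for this trial. Baseline adjustment clearly reduces the problem but need not remove it. The estimate of the condition effect on the primary outcomes does not depend on this path.

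**What to change.** In SAP 1.2.1:

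1. Define time zero of all growth factors as the first follow-up (1 month), so that baseline is a covariate and not a modelled wave. Otherwise adjusting a baseline intercept for its own baseline value would be circular.
2. In every mediation model, regress both the mediator and the outcome growth factors on condition, the baseline value of that mediator and the baseline value of that outcome. Use this adjusted model in the bootstrap and constraint tests.
3. Report any indirect effect as assuming no unmeasured mediator-outcome confounding, with a simple sensitivity analysis showing how much residual confounding would remove it.

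The cost is SAP wording and two extra parameters per equation. Baseline outcomes are already used in the randomisation check, and Aim 1b already relies on baseline communication, so no visit is added. The estimated indirect effect will probably be smaller, and the power claimed for the indirect pathways will be less favourable.
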